8.4 Final Visit

The Final Visit (36 weeks PMA or discharge, whichever comes first) will include the following:

1. Documentation of respiratory support and supplemental oxygen (Section 7.6)
2. AEs, including ADEs (Section 9)
3. Physical examination (including changes from baseline exam) (Section 7.1.6)
4. Occurrence or presence of the following (as applicable):
 - a) IVH (worst grade during hospitalization)
 - b) Cystic PVL during hospitalization
 - c) PDA and related treatments (surgery or pharmacologics)
 - d) NEC (stage and related treatments)
 - e) Lung air leaks
 - f) Pulmonary hemorrhage
 - g) Acquired sepsis
 - h) Apnea
5. Incidence of BPD
6. The incidence of ROP (Appendix 5) (document onset and severity throughout study participation)
7. Survival (date, time, and cause of death if applicable)

8. Date and time of transfer or discharge from the current hospital (if applicable)
9. Concomitant medications (Section [7.3](#))

9 ADVERSE EVENT REPORTING

Information regarding the occurrence of AEs, including ADEs, will be assessed from the time of randomization until completion of Final Study Visit.

For purposes of this study, the following will be considered AEs of special interest if they occur within the primary observation period:

1. Bradycardia: defined as a heart rate < 100 bpm for ≥ 20 seconds
2. Desaturation: defined as $SpO_2 < 80\%$ for ≥ 20 seconds
3. A sustained apnea event defined as lasting ≥ 20 seconds and is coincident with at least one of the following: (1) HR < 100 bpm, (2) desaturation (oxygen saturation $< 80\%$), (3) requirement for intermittent positive pressure breaths using inflating pressures above the set CPAP pressure administered manually or mechanically through any patient interface.
4. Air leak, including pneumothorax and pneumomediastinum.

Complications related to placement of bi-nasal prongs as identified by the following:

- Bleeding
- Apparent obstruction of the nares
- Occlusion of the interface requiring removal and replacement
- Nasal irritation (erythema of nares or septum, inflammation of nares or septum)

All AEs must be followed by the PI until resolution or for at least 30 days post-study if the subject is stable.

Documentation of AEs in the eCRF must include the following parameters; (1) duration (time of onset and resolution), (2) severity or grade, (3) outcome, (4) action taken, and (5) relationship to study drug and/or device.

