3.1 Primary Objective

The primary objective of this study is to evaluate the safety and tolerability of lucinactant for inhalation, administered as an aerosolized dose in 4 escalating doses to a preterm, neonatal population 26 to 28 completed weeks PMA receiving nCPAP for RDS compared with neonates receiving nCPAP alone.

Safety and tolerability will be evaluated using the same measures and assessments that have been used in Protocol 03-CL-1201, which has shown lucinactant for inhalation up to 75 mg/kg to be generally safe and well-tolerated in infants 29 to 34 completed weeks PMA.

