8.2 Primary Observation Period

The following will be documented for each randomized subject during the Primary Observation Period of the study (≤ 48 hours after randomization [T_0]):

1. Date and time (T_0) of randomization and the study dosing group assignment (Section 5.2.2)
2. The date and time of the initiation and completion of aerosol delivery (Section 5)
3. All AEs, including ADEs (Section 9)
Peri-dosing events (defined as an AE with an onset time ≤ 2 hours from the time of initiating administration of lucinactant for inhalation) may include but not be limited to:
 - Bradycardia (as noted by HR < 100 bpm for ≥ 20 seconds) (Section 7.1.1)
 - Desaturation (as noted by O₂ saturation $< 80\%$ for ≥ 20 seconds) (Section 7.1.3)
 - Gagging/regurgitation
 - Apnea (central, obstructive, or combined) (Section 7.1.1)
 - Pallor
 - Complications related to placement of bi-nasal prongs (bleeding, apparent obstruction of the nares, bi-nasal prongs occlusion requiring removal and replacement, nasal irritation).
4. Respiratory support and supplemental oxygen as outlined in Section 7.6
5. nCPAP settings (Section 5.4), (Section 7.6)
6. FiO₂ values (Section 7.1.4)
7. Signs and symptoms consistent with worsening of respiratory status (Section 7.5)
8. Vital signs and SpO₂ (Section 7.1.1, Section 7.1.3)
9. PCO₂ values (Section 7.1.5)
10. Chest radiograph, as applicable (Section 7.1.8)
11. Gastric liquid volume (Section 7.1.9)
12. Serum electrolytes (Section 7.1.7)
13. Defecation (initial 24 hours following randomization) (Section 7.1.10)
14. Concomitant medications (Section 7.3)
15. Technical performance of the device (Section 5.1.4)
16. The use of pacifiers

8.3 Extended Observation Period:

The following assessments are to be performed during the Extended Observation Period of the study (> 48 hours to ≤ 7 days after date of randomization). Daily measurements are to be obtained as close to 0800 as possible.

1. Assessment and documentation of respiratory support and supplemental oxygen (Section 7.6)
2. Signs and symptoms consistent with worsening of respiratory status (Section 7.5)
3. Vital signs (Section 7.1.1)
4. SpO₂ (Section 7.1.3)
5. Chest radiograph, as applicable (Section 7.1.8)
6. Incidence of AEs, including ADEs (Section 9)
7. Concomitant medications (Section 7.3)

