NIPPV	Nasal Intermittent Positive Pressure Ventilation includes all forms of nasal ventilation; bi-level, synchronized, or continuous. NIPPV cannot be used to qualify the infant or be used during aerosol treatment.
Oxygen, off supplemental	Neonates who do not require any form of supplemental oxygen for ≥ 24 hours. Neonates requiring oxygen only during feeding are considered off supplemental oxygen.
Oxygen, other delivery modes	Includes all modes of non-pressure support (nasal cannula, oxygen hood, etc.)
Oxygen, supplemental	Any requirement for additional oxygen (FiO ₂ > 0.21).
Period, extended observational	The study timeframe occurring > 48 hours from randomization until ≤ day 7
Period, final observational	The study timeframe occurring > day 7 to ≤ 36 weeks PMA
Period, primary observational	The study timeframe occurring ≤ 48 hours from randomization
Periventricular leukomalacia (PVL)	The presence of one or more echolucent cysts in and around the cerebral ventricles noted on cranial ultrasounds. This is not the early presence of bright echogenic areas (known as “flares” or periventricular “echodensities”).
Physical exam	Includes the following organ systems: cardiac, respiratory, abdomen, genitalia and perineum, skin, extremities, head, neck and mouth, and neurological.
Pressure support	Includes all modes of pressure support (IMV/SIMV, AC, HFV, CPAP, etc.)

Definitions	
Pulmonary hemorrhage	The presence of bright red blood in a tracheal aspirate deemed not to be the result of tracheal trauma, associated with deterioration in the subject's condition and a change in chest radiographs.
Study dosing	The randomized to receive 1 dose of lucinactant for inhalation through an investigational ADU device for either 30 or 45 minutes in conjunction with the protocol required nCPAP support.

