- ⁸ Serum electrolytes are to be evaluated 24 hours from randomization (± 6 hours) (Section 7.1.7)
- ⁹ Gastric liquid volume will be assessed 30 minutes (± 15 minutes) following completion of lucinactant for inhalation administration. Enteral feedings are to be held during and ≥ 1 hour following completion of lucinactant for inhalation administration (Section 7.1.9).
- ¹⁰ Peri-dosing events are defined as any adverse event with an onset time ≤ 2 hours from the time of initiating administration of lucinactant for inhalation

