1.2.3 Safety Evaluations

The following measures are to be documented in the electronic case report form (eCRF) in accordance with timings outlined in study schedule:

1. Survival (date and time of death if applicable)
2. AEs, including ADEs
 - To include: nasal excoriations by examination (≥ 24 hours to ≤ 7 days following aerosol exposure) and evidence of lung air leak (especially pneumothorax)
 - To be categorized as a peri-dosing events if onset of event is ≤ 24 hours from the time of initiating administration of lucinactant for inhalation
3. Signs consistent with worsening respiratory status
4. Concomitant medications
5. Use of respiratory support and supplemental oxygen to include:

- Need for endotracheal intubation and mechanical ventilation
 - Need for intermittent positive pressure breaths using inflating pressures above the set CPAP pressure administered manually or mechanically through any patient interface
6. nCPAP and fraction of inspired oxygen (FiO₂) requirements
 7. Complications of prematurity (ie, IVH, periventricular leukomalacia [PVL], pulmonary hemorrhage, NEC, patent ductus arteriosus [PDA], sepsis, ROP, BPD)
 8. Physical examinations
 9. Tolerability of lucinactant for inhalation
 10. Incidence leading to withdrawal from study
 11. Incidence of air leak
 12. Assessments of the following:
 - a) PCO₂
 - b) Serum electrolyte measurements
 - c) Body weight
 - d) Vital signs
 - e) Gastric liquid volume
 - f) Defecation
 - g) Oxygen (O₂) saturation, as determined by pulse oximetry (SpO₂)
 - h) Chest radiography, as applicable

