¹⁰ Peri-dosing events are defined as any AE with an onset time ≤ 2 hours from the time of initiating study treatment.

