6.4.1 Peri-Dosing AEs

The incidence of peri-dosing events (bradycardia, desaturation, and vomiting) will be summarized. In addition, the incidence of complications related to the placement of bi-nasal prongs (bleeding, apparent obstruction to the nares, occlusion of the prongs, nasal irritation, and other) will be summarized. Peri-dosing events and complications related to the placement of the prongs will also be summarized with all adverse events.

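### The SAP has no output on the protocol's 0-48 h window for AEs of special interest, its safety population literally omits the nCPAP-only controls, and one section gives the wrong peri-dosing window.

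*Protocol*

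**What the plan says.** **Definition.** Protocol Section 9 numbers four events: bradycardia and desaturation (each lasting at least 20 seconds), sustained apnea, and air leak. It states that "the following will be considered AEs of special interest if they occur within the primary observation period". Appendix 1 defines that period as "The study timeframe occurring ≤ 48 hours from randomization", and Section 8.2 applies it to both arms: "The following will be documented for each randomized subject during the Primary Observation Period of the study". A list of bi-nasal prong complications follows the four items without a number, so it is unclear whether they belong to the category.

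**Objective.** Protocol Section 3.1 asks for safety and tolerability "compared with neonates receiving nCPAP alone".

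**Planned counts.** The SAP never uses the special-interest category. Its Section 6.4.1 says: "The incidence of peri-dosing events (bradycardia, desaturation, and vomiting) will be summarized". The same section also sends these events into the all-AE summaries.

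**Peri-dosing window.** SAP 1.2.3 classes an event as peri-dosing "if onset of event is ≤ 24 hours from the time of initiating administration of lucinactant for inhalation". SAP 2.2.4 says instead: "Peri-dosing events are defined as any AE with an onset time ≤ 2 hours from the time of initiating study treatment". Protocol Appendix 2 agrees with the latter: "Peri-dosing events are defined as any adverse event with an onset time ≤ 2 hours from the time of initiating administration". Protocol 3.3 and 8.2 and the SAP Executive Summary also give 2 h.

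**Population.** SAP 6.1 limits the safety population to infants given study drug and bases all safety assessments on it. The SAP Executive Summary, the Protocol Summary and Protocol 13.1 base the analysis on all randomized infants.

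**The concern.** The protocol sets up an acute safety category on a clock that does not depend on treatment, and the primary objective is a comparison with nCPAP alone. The SAP then reports acute bradycardia and desaturation on a clock that starts with dosing. Controls are never dosed, and the SAP gives them no substitute start. It does give them one elsewhere: randomization serves for baseline (9.1) and for gastric volume (6.5.4).

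At stake is a like-for-like count, in the final tables, of the events most likely around aerosol delivery. If SAP 6.1 were programmed as worded, there would be no control column in any safety table. If SAP 1.2.3 were programmed, Table 6.1 would not match the protocol's definition.

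**Working it through.** The plan has no figure to reproduce: SAP 2.2.3 says no sample size calculation was done, and no AE rates are assumed. The check sets the outputs side by side and then does the window arithmetic.

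**1. Which output captures what**

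| SAP output | Time zero and window | Bradycardia or desaturation episodes against control? |
|---|---|---|
| Table 6.1, peri-dosing | Start of treatment; 2 h (24 h by SAP 1.2.3) | Episodes, but no time zero for controls |
| Tables 6.3.1-6.3.5, all AEs | AEs collected from randomization (Protocol 9); no cut; treatment-emergent not defined | Episodes by arm, but not acute |
| Table 4.1.1, early worsening | Birth; 72 h; ITT population | Only if a worsening criterion is met |
| Tables 6.2 and 7.8 | No time cut | Air leak (both) and apnea (7.8) only |
| Tables 7.1.3 and 7.5.2 | Scheduled heart rates; SpO2 over 72 h | Values, not episodes of 20 seconds or more |

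**2. How far Table 4.1.1 reaches.** Randomization is at most 20 h after birth, so the 48 h window closes by 20 + 48 = 68 h, inside 72 h. Its criteria (SAP 4.3.2) include sustained apnea, positive-pressure breaths, nCPAP above 7 cm H2O, sustained FiO2 above 0.50, intubation and investigator judgment. What remains uncovered is bradycardia and desaturation that meet none of these.

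**3. Peri-dosing window against 48 h**
- Hours outside it: 48 − 2 = 46 h; with the 24 h version, 48 − 24 = 24 h; with two 2 h windows after a repeat dose, 48 − 4 = 44 h.
- Time covered after dosing ends, Groups I to IV: 120 − 30 = 90, 120 − 45 = 75, 120 − 60 = 60, 120 − 90 = 30 min.
- Earliest repeat dose (Group I): 0.5 + 2 = 2.5 h after the first start, so outside the first 2 h window.
- Latest end of a repeat dose (Group IV, taking 24 h as the limit on its start): 2 + 1.5 + 24 + 1.5 = 29 h after randomization. The 48 h window still has 48 − 29 = 19 h to run.

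**4. All-AE window.** From 26w0d or 28w6d to 36w0d is 70 or 50 days at most. The 48 h share is 2/70 = 2.9% to 2/50 = 4.0%.

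**5. Dilution, illustration only.** Let pA and pC be the 48 h risks. Assume a later risk b that is equal in both arms and independent of the early event, and count infants ever affected:

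[1 − (1 − pA)(1 − b)] − [1 − (1 − pC)(1 − b)] = (pA − pC)(1 − b)

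With assumed risks of 60% and 30%, the 30-point gap becomes 15 points at b = 50%, 6 at 80% and 1.5 at 95%. At b = 10%, 90% of the gap is kept. None of these rates is in the documents.

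**6. Population.** SAP 6.1 as worded gives about 32 active and 0 control infants. All randomized gives about 32 and 32.

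**7. Precision and ascertainment of a 48 h table.** One infant is 1/8 = 12.5 points in a dose group and 1/32 = 3.1 points in an arm. The exact 95% upper limit for no events is 37% at 0/8 and 11% at 0/32. Protocol 7.1.1 and Appendix 2 have heart rate documented during active dosing every 5 min (Groups I and II) or every 15 min (III and IV). That is about 30/5 = 6, 45/5 = 9, 60/15 = 4 and 90/15 = 6 readings, against one extra reading in controls.

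**The case against.** Side-by-side counts already exist. SAP 6.4 gives every AE by treatment group as frequency and percent, and AE collection starts at randomization in both arms, so only the 48 h cut is missing. Table 4.1.1 picks up the acute events that led to escalated support, on the ITT population. The study is descriptive, and SAP 6.4 says AEs are not compared between groups. All of this stands and limits the point. The last item does not bar the table, because a side-by-side display needs no test.

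A 48 h table would also not be matched on observation. Active infants are watched more closely during dosing in an open-label trial, which can inflate their bradycardia count, and up to 2 h of their window precedes dosing. This stands too. It calls for a footnote, not for leaving the table out.

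Protocol 13.1 promises summary statistics for all variables by dosing group. That is too general to rely on: it names no special-interest or 48 h output, and Section 13 refers to the SAP for the full set of analyses.

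A reader might infer three stronger things that the documents do not support:
- **That controls will be dropped.** The treatment-group definition (SAP 2.2.1), the randomization anchor for gastric volume (6.5.4) and Figures 2.1-2.3 show they are meant to be included. The fault is in the wording.
- **That the all-AE tables count each infant once per term and so hide an early excess.** SAP 6.4.3 introduces that rule for AEs other than those already listed, so its application to bradycardia and desaturation is not settled.
- **That the safety committee lacks these events.** Protocol 6.1 and 13.2 give it all AEs and the AEs related to dosing. Its data cut is unmatched (72 h for active infants, whatever is available for controls), but the information reaches it.

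**Conclusion.** The point holds as a gap in planned output plus two SAP rules that are wrong as written. These should be corrected. The gap is narrow: it concerns bradycardia and desaturation that meet no worsening criterion. Air leak loses only its timing, and sustained apnea is largely covered.

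Confidence is high that the table is missing and that Sections 6.1 and 1.2.3 conflict with the other text. It is not high on harm. The 46 uncovered hours count time, not events. The dilution result depends on assumed, equal and independent later risks. If infants without an early event also have a lower later risk, more of an early difference would survive in the all-AE tables than the formula shows. The documents therefore do not support a claim that an early excess would be masked, only that the planned final tables could not show it on the protocol's own window.

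**What to change.** 1. **SAP 6.1:** define the safety population as all randomized infants, or as treated with nCPAP-only controls explicitly included.
2. **SAP 1.2.3:** change 24 h to 2 h, and state that the window restarts at a repeat dose.
3. **SAP 6.4 and Section 11:** add one descriptive table of the Section 9 AEs of special interest with onset 0-48 h from randomization. Show infants (n, %) and episodes by active dose, all active and pooled control. State whether bi-nasal prong complications are included.
4. **Footnotes to that table:** small cells (12.5 points per infant at 8, 3.1 at 32), up to 2 h undosed at the start of the active window, and closer heart-rate documentation of active infants during dosing.

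The cost is SAP wording and one table. AE onset times are already in the eCRF (Protocol 9), so no new data, infants or tests are needed.

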9.1 Adverse Events

An AE is defined as any untoward medical occurrence in a study subject who is administered a pharmaceutical product that does not necessarily have a causal relationship with this product. An AE can therefore be any unfavorable and unintended sign (including an abnormal laboratory finding), symptom, or disease temporally associated with the use of an investigational product (drug and/or device), whether or not related to the investigational product (see ICH guideline E2A *Clinical Safety Data Management: Definitions and Standards for Expedited Reporting*).

An ADE is an AE related to the use of the investigational device. ADEs are treated the same as all other AEs. For serious ADEs, see unanticipated adverse device effects (UADE) in Section 9.1.5.

9.1.1 Causal Relationship of Adverse Events

The relationship of an AE to a study drug is assessed by the PI using the following definitions:

- Not related: The AE is clearly related to other factors, such as the subject's clinical state, therapeutic interventions, or concomitant drugs.
- Unlikely Related: The AE was most likely produced by other factors, such as the subject's clinical state, therapeutic interventions, or concomitant drugs, and does not follow a known response pattern to the study drug.
- Possibly Related: The AE follows a reasonable sequence from the time of drug administration and/or follows a known response pattern to the study drug, but could have been produced by other factors, such as the subject's clinical state, therapeutic interventions, or concomitant drugs.
- Related: The AE follows a reasonable temporal sequence from the time of the drug administration and meets the following criteria;
 - a) Follows a known response pattern to the study drug
 - b) Cannot be reasonably explained by other factors such as the subject's clinical state, therapeutic interventions, or concomitant drugs
 - c) Meets one or more of the following:
 - occurs immediately following study drug administration
 - improves on stopping the drug
 - reappears on repeat exposure
 - there is a positive reaction at the application site.

9.1.2 Severity Grade Levels of Adverse Events

The severity of an AE is assessed by the PI using the following definitions:

- Mild: Symptoms causing no or minimal interference with usual social and functional activities
- Moderate: Symptoms causing greater than minimal interference with usual social and functional activities
- Severe: Symptoms causing inability to perform usual social and functional activities

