Dose assignments will be un-blinded, as the primary objective of this study is safety and tolerability. Preliminary efficacy endpoints will be assessed as an exploratory objective.

All enrolled subjects will receive study treatment in a neonatal intensive care unit (NICU) , a specialized care center staffed by neonatologists, nurses, and respiratory therapists who are experienced in the delivery of emergent care to the preterm neonatal population. Infants in the NICU are continuously monitored using advanced and sophisticated monitoring equipment, and there is ready and immediate access to equipment, medications, and skilled personnel that may be needed to address emergent developments. Interventions such as endotracheal intubation, mechanical ventilation, and surfactant administration will be readily available to all study subjects if clinically indicated in accordance with the high level standard of care customary in the NICU.

Neonates will be followed through the primary phase evaluations through 36 weeks PMA, NICU discharge, hospital transfer, or death, whichever occurs first.

Study Population:

This study will be comprised of preterm neonates 26 to 28 completed weeks PMA who are receiving care in a NICU and are eligible to receive nCPAP support for RDS.

The study population will consist of 4 escalating dose groups with an allowed repeat dose if repeat dose criteria are met. Repeat dosing is to ensure subjects with a demonstrated need will receive additional treatment, as is done with bolus dosing.

- Study Sample Size:** It is anticipated that approximately 64 subjects will be enrolled. Approximately 32 subjects will be randomized to the active arm (drug/device combination) and approximately 32 subjects will be randomized to the control arm (nCPAP alone).
- The sample size is based on the number of subjects necessary to evaluate safety and tolerability of lucinactant for inhalation. Sample size calculations to demonstrate a clinical effect will not be performed as efficacy is an exploratory objective. Subjects that do not complete the administered dose of lucinactant for inhalation, or withdraw from the study will not be replaced, unless required by the SRC in order to adequately assess safety in the dose group.
- Number of Sites:** Up to approximately 25 clinical sites in the US; sites outside the US may also be used.

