6.4.3 Other AEs

AEs, other than those listed above, will be summarized by the MedDRA preferred term and SOC for all AEs, regardless of relationship to study drug, and for AEs at least remotely related. If an AE occurs multiple times for the same subject within the same term or body system, only the most severe occurrence for that term or body system will be counted.

In addition, all AEs will be summarized by severity (mild, moderate, severe), relationship to the study drug (unrelated, unlikely related, possibly related, definitely related), whether or not the AE was device related, gender, race, and ethnic origin.

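### AE severity has no anchor that can be observed in a 26 to 28 week neonate, so the planned severity outputs have no defined or reproducible meaning across sites

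*Protocol*

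**What the plan says.** Protocol 9.1.2 gives the investigator a closed set of definitions: "The severity of an AE is assessed by the PI using the following definitions". The lowest of the three grades reads "Symptoms causing no or minimal interference with usual social and functional activities". The middle grade asks for more than minimal interference of the same kind, and the highest for being unable to carry out those activities at all.

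The Protocol Summary describes the study population as "preterm neonates 26 to 28 completed weeks PMA who are receiving care in a NICU". They are randomized within 20 hours of birth.

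Protocol Section 9 makes the grade a required field for each AE ("2) severity or grade"), alongside others such as outcome and "4) action taken". SAP 6.4.3 then uses it: "all AEs will be summarized by severity (mild, moderate, severe"). The same section counts only the worst-graded occurrence when a subject has repeats within a term or body system. SAP 6.4.4 applies a similar rule to SAEs and lists their severity.

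**The concern.** The scale presupposes a subject with a daily life that can be disturbed. A neonate under 20 hours old on nCPAP has none that an investigator can observe, so the criterion gives no way to choose between the grades. An investigator must either leave events undifferentiated or supply a personal reading, and two sites can grade the same event differently while both follow the protocol.

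What is at stake is the meaning of the severity outputs in a study whose primary objective is safety and tolerability. The grading is open-label and spread over approximately 25 sites. Dosing groups enroll one after another, so a change over time in how sites grade could look like a difference between doses. Each dosing group has concurrent controls, but the SAP combines all controls into a single column.

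**Working it through.** The plan gives no figure to reproduce. The check is of the text, with one small piece of arithmetic on sensitivity.

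**1. Criterion against population.** All three grades in Protocol 9.1.2 rest on the same activity criterion, and none has a second anchor such as intervention, duration or change in clinical status. The wording also grades symptoms, whereas the AE definition in Protocol 9.1 extends to signs and abnormal laboratory findings.

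**2. Is there another general scale?** None was found in either document.

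- Protocol Appendices 3 to 5 give neonatal grading for IVH, NEC and ROP only.
- Protocol 7.1.1, 7.1.3 and 9 set thresholds for bradycardia, desaturation and sustained apnea. These decide whether an event occurred, not how severe it was.
- Protocol 7.7 defines acute respiratory deterioration but does not grade it.
- SAP 6.4.3 and 6.4.4 use the severity categories without redefining them.

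**3. Where the grade is used.**

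- SAP Table 6.3.2 (by system organ class, term and severity) and Table 6.3.4 (by severity and relationship), which are 2 of the 39 tables listed in the SAP.
- The SAE listing described in SAP 6.4.4.
- The choice of which repeat occurrence is counted (SAP 6.4.3 and 6.4.4). If repeats were attributed differently to study drug, this choice could also decide which relationship is tabulated.

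**4. Where it is not used.**

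- Subject-level incidence: a subject with several events under one term counts once, whichever occurrence is kept.
- Seriousness, which has its own criteria in Protocol 9.1.4.
- The enrollment holds in Protocol 6.2 and SAP 7.2, which turn on related SAEs and on related death within 12 hours.
- The review inputs named in Protocol 6.1, and the safety endpoints in Protocol 3.3 and SAP 6.2, none of which names the mild/moderate/severe grade.
- IVH, NEC and ROP staging (SAP 6.5.8).

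**5. Sensitivity of a severity cell.** The number of misgraded events cannot be derived. The effect of one regraded subject can, using the planned group sizes:

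- Active dose group, n = 8: 1/8 = 12.5 percentage points.
- Combined controls, n = 32: 1/32 = 3.1 percentage points.

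Subjects per site are 64/25 = 2.6 with the site count in Protocol 4.1, or 64/12 = 5.3 with the count in Protocol 2.3. With so few per site, site grading habits have little chance to average out within a dose group of 8.

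**The case against.** The strongest reply is that the grade carries little weight here. No hold rule or listed safety endpoint uses it, there is no hypothesis testing, and SAP 6.4 says AEs will not be compared between treatment groups. This stands, and it limits the point to the severity outputs.

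A reader might infer more, in four ways that the documents do not support:

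- *That the severity tables cannot be valid at all, or that every site must invent a scale.* An investigator could read functional activity as breathing or feeding. AE pages are completed under eCRF guidelines supplied separately (Protocol 9.1.3), whose content is not available. SAP 6.4 also has AEs reviewed by the medical monitor or designee, though it does not mention regrading. What can be said is that neither document fixes a common reading.
- *That severity by dose is a main descriptor of tolerability.* Protocol 6.2 bases failed tolerability on AEs, particularly those related to administration, without mentioning the grade.
- *That a brief desaturation could not be told apart from a pneumothorax.* They are different terms, reported separately in SAP Tables 6.1 and 6.2. The loss is in grading within a term, and in Table 6.3.4, which pools across terms.
- *That all AE data are compromised.* One field per record is affected. Duration, outcome, action taken and relationship are recorded separately.

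It is also fair to object that a better scale would still be applied by investigators who know the arm, and that anchors based on care decisions are themselves open to that influence. A new definition repairs the missing meaning, not the lack of masking.

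**Conclusion.** The concern holds in limited form. The only general severity scale relies on something that cannot be observed in this population. The investigator grades, SAP Tables 6.3.2 and 6.3.4, the severity entry in the SAE listing and the selection of the worst-graded occurrence therefore have no defined or reproducible meaning across sites.

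The extent of misgrading is unknown. One subject's grade is worth 12.5 percentage points in an active dose group. The conclusion assumes that the unseen eCRF guidelines do not supply a neonatal scale. If they do, the remaining task is to bring that definition into Protocol 9.1.2, which presently directs investigators to different wording. This merits correction before enrollment but is not a reason to hold the study.

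**What to change.** Before first enrollment, rewrite Protocol 9.1.2 with severity anchors observable in a neonate. Examples are change from baseline clinical status and level of intervention needed, drawing on the action-taken and outcome fields already collected. Two conditions apply:

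- Exclude protocol-scheduled monitoring, because it differs by arm. Under Protocol Appendix 2, active subjects have vital signs every 5 or 15 minutes during dosing, against one additional reading at 15 minutes after randomization for controls.
- Keep severity separate from the seriousness criteria in Protocol 9.1.4.

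Settle the final wording with the medical monitor, cite it in SAP 6.4.3 and 6.4.4, and include it in site training. This alters a measurement definition, not patient care.

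The direct cost is revised protocol and eCRF-guideline text and a training item. Protocol Section 3 keeps endpoints the same as Study 03-CL-1201 so that results may be compared and pooled. The documents do not show which severity scale that study used. If it used the present one, severity grades (though not AE incidence) would not pool directly, and the study report should say so.

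If events have already been graded, label the severity tables as uncalibrated investigator judgment.
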